#### **Corticography Protocol:**

Equipment Needed:

1. Nicolet EEG Portable Acquisition unit
2. **C64** Amplifier
3. 2 x sterile Grass monopolar needle electrodes (1 – ground, 1 – reference)
4. 2 x Touch-proof adapters for needle electrodes
5. 64-lead sterile Ad-tech electrode cable
6. 4 x sterile 16-contact Ad-tech connector blocks
7. 64-contact (8x8) Ad-tech electrode; spacing as follows:
  - a. If lesion is <=2 cm in maximal dimension, use grid with 5mm spacing
  - b. If lesion is 2.1-3 cm in maximal dimension, use grid with 7.5mm spacing
  - c. If lesion >3cm in maximal dimension, use grid with 10mm spacing

Anesthesia:

**Remifentanil/propofol.** If using volatile anesthesia, turn off 15 minutes prior to beginning recording.

Procedure:

1. Wheel portable EEG station into room, turn on and enter patient demographics as per routine
2. Configure 64-electrode montage in NicOne
3. Neurosurgeon to place ground and reference electrodes in scalp muscle adjacent to craniotomy
4. Neurosurgeon to photograph lesion

CONFIDENTIAL

This document and information is the property of the NYU School of Medicine and Langone Medical Center. Do not disclose or use except as authorized in writing by the study IND sponsor

5. Neurosurgeon to place selected subdural grid electrode with center of grid overlying approximate center of the lesion
6. Neurosurgeon to connect and pass 64-contact Ad-tech adapter to neurophysiologist who will connect it to C64 amplifier
7. Record ECoG for a minimum duration of 10 minutes using the following settings: High Pass Filter 1 Hz, Low Pass Filter 70 Hz, Gain 70uV/mm, notch filter off.
8. Neurosurgeon to place paper markers on 4 corners of grid then remove the grid and photograph the brain again.
9. Save ECoG file as anonymized file without video to external hard drive using subject number as file name.
10. Obtain intraoperative photos from neurosurgeon and relabel by subject number, XXXX\_pregrid, XXXX\_grid and XXXX\_postgrid. Save files to external hard drive

#### **5.10 Visit 4 (and all days with invasive electrodes) NYU Tisch Hospital**

The day after surgery, and every day thereafter if invasive electrodes are utilized:

- The research subject will be seen by a board-certified neurosurgeon or study designee and evaluated for evidence of infection and abnormal wound healing as per the protocol (including digital photographs of the surgical site dressing) in both treated and untreated comparison groups.
  - We will take photographs of the surgical site dressing and subject's face will not be in the photo. All photos will be de-identified in the same manner all of their clinical information for this study will be de-identified. Consent for the photographs are part of the consent form. The photographs will not be shared with anyone outside of the research team or anyone who is not a part of the patient's medical care.
- A board-certified neurologist/epileptologist will also evaluate the subject daily while invasive electrodes are used.
  - All seizures and subclinical electrographic seizure discharges will be reviewed and the type (e.g., simple v. complex partial v. subclinical electrographic discharge), onset region(s), spread zone(s), and duration.
  - Each day a standard portion of the awake and sleep EEG records and all seizures, including the period for one minute before seizure onset and 5 minutes after seizure offset will be stored and available for subsequent analysis.

The neurologist/epileptologist or study designee will record vital signs and perform a physical and neurological examination and inquire about potential adverse events.

#### **5.11 Visit 5a (Active and concurrent comparison group) (if a second surgery is done at the end of invasive recordings) NYU Tisch Hospital**

Resected tissue at the time of surgery will be distributed by the Pathology Departments at the local institutions and samples will be used for investigation per the IRB-approved protocol. This tissue will be used for research analysis of biochemical, molecular, electrophysiological, and genetic measures.

6.5a Resected brain tissue will be distributed at the Pathology Department of the NYU Medical Center then stored in the Alexandria Center for Life Sciences, located at [name] on 9th floor a -80 freezer until requested to be analyzed..

The samples will be de identified and coded so that [name] will have access to the key. The samples will be stored and used only for analysis for this study. All tissue remaining after this study will be kept in our bank or destroyed per individual patient voluntary consent.

Samples will be stored secure labs in the above addresses. Our 3 NYU Pathologists-internal collaborators, [name], [name], and [name]) will perform analysis of brain resection specimens from patients on this study, and will be used for preparation of DNA/RNA assays. They will be looking for mutations in mTOR pathway genes. The samples will be studied using next gen sequencing, proteomics and/or Micro RNA assays, to search for mutations which may have caused the tuber or cortical dysplasia (CD). This analysis will focus on genes known to be involved in tuber/CD development including TSC1, TSC2, AKT1, AKT2, AKT3, MTOR, PTEN. Any variants that are found will be compared

CONFIDENTIAL

with those found in blood DNA samples from the same subjects. If subjects have indicated an interest in learning of the genetic findings, the findings will be provided to them. This information will be offered to the patients and their families through a physician or genetics counselor experienced with tuberous sclerosis. As this is not a clinical grade (CLIA-certified) analysis, the findings will be presented as research findings, which must be confirmed by a CLIA lab if any clinical action were considered based upon the information. The results of the genetic analysis will not be shared with anyone outside of the research team. The use of samples for this study is required.

Our 3 pathologists mentioned above will be assaying mTOR pathway activation using immunochemistry, western blotting analysis, and capture ELISA and other biochemical and molecular biology techniques, in order to obtain such results. He will be looking at levels of mTOR signaling proteins in lymphocytes of human blood specimens. 2 mls in purple cap EDTA tube will suffice. For all Biochemical assays we will utilize fresh frozen tissue, For Immunohistochemistry fixed frozen tissue in 4% PFA and sucrose sink 48hrs and frozen using OCT blocks can be used. The panel of Abs used for detection will be a panel of set-fixed 6 to 10 antibodies. Up to 5mg of tissue will be adequate for MTA purposes and research result solidity.

They will be looking for biomarkers of inflammation, and cytokines. She will measure the changes in serum HMBG1 with brain tissue expression. She will also measure miRNAs in serum using additional 100-200 microliters of serum from each patient, as well as brain tissue from specified post – resection pathological TSC, or / and Epilepsy patients, and collected under an Approved ICF and under the supervision of the BRC of NYULMC (in order to distribute),

If subjects wish to withdraw from this portion of the study, they will need to write a formal letter to the Principal Investigator stating why they would like to withdraw and we will withdraw them after that, having their sample destroyed. The withdrawal procedures will be explained to them when they are signing the consent form.

#### **5.12 Visit 5b Active and concurrent comparison group) (postoperative day 2 and all days until discharge) NYU Tisch Hospital**

Each postoperative day while the research subject is in the hospital, they will

- Be seen by a board-certified neurosurgeon or study designee and evaluated for evidence of infection and abnormal wound healing as per the protocol (including digital photographs of the surgical site dressing).
- Be seen by a board-certified neurologist/epileptologist or study designee who will also evaluate the subject daily each day to inquire about potential adverse events.

CONFIDENTIAL

This document and information is the property of the NYU School of Medicine and Langone Medical Center. Do not disclose or use except as authorized in writing by the study IND sponsor

### **5.13 Visit 6 (Active and concurrent comparison group) NYU CEC**

3 to 10 days after discharge, the research subject will:

- Be examined by a board-certified neurosurgeon or study designee and evaluated for evidence of infection and abnormal wound healing as per the protocol (including digital photographs of the surgical site dressing).
- Be examined by a board-certified neurologist/epileptologist or study designee to review current medications, any adverse events, and perform a physical and neurological examination.

## **6 Statistical Plan**

### **6.1 Sample Size Determination**

#### **Statistical Methods**

Distributions of patient and disease characteristics will be summarized descriptively at study entry by dose duration cohort and across cohorts in the everolimus group and in the comparison group. Frequency distributions and cross tabulations will be presented for categorical variables. For continuous variables, summary statistics (means, medians, interquartile ranges, standard deviations, etc) will be provided along with graphical displays (e.g., boxplots) by treatment group.

Safety will be summarized within and across dose duration cohorts and compared with the events in the comparison group.

S6 phosphorylation levels in brain tissue sample at surgery will be summarized descriptively for each dose duration cohort and across cohorts in the treated group and in the comparison group. Further, levels will be compared between the treated and comparison group using 2 sample 2 sided t-tests (with appropriate transformations of levels if required to meet the assumptions of the method).

Similar analyses will be carried out for all additional continuous endpoints of interest. No adjustments for multiplicity will be made in this small study. Bivariate scatterplots and correlation coefficients will also be provided to examine the associations between the multiple endpoints.

#### **7.3 Subject Population(s) for Analysis**

All patients who receive one or more doses of drug will be included in the analyses of safety. Those patients who undergo surgery will be included in the analyses of S6 phosphorylation and other measurements obtained at the time of surgery. Additional analyses will be conducted to compare those subjects who did not complete treatment and surgery with respect to disease and patient characteristics to identify any potential differences between these groups of patients.

7. Sample size considerations. For this preliminary study, safety analyses are primary. Study termination will occur if, among the 9 treated subjects, there are two cases of wound healing problems or three cases of serious infection, including wound site infection. In the case of a wound site infection, any problems with wound healing will be considered secondary to the infection and NOT as a primary wound healing problem. These estimates are based on neurosurgical experience and reports with the frequency of wound healing problems of <2% and infection from 1.6 to 8.6% in six published series, with a mean infection rate of 5.3%. [33-38]

For the analysis of S6 phosphorylation, based on a 2 sample 2 sided t-test, we can detect a difference of  $|1.4| - |1.5|$  standard deviations between the comparison controls and the treated group with 9 treated subjects with alpha = 0.05 and power of 80%. Preliminary data using quantitative Western blots obtained from 4 resected tubers demonstrated phospho-S6/S6 ratios of 257 ± 42% of control. With 9 treated subjects, and 12 controls, we would be able to detect a 62 – 65% difference in phospho-S6/S6 levels between treated and untreated groups, which is likely a biologically meaningful difference. Prior studies in murine models of TSC treated with rapamycin have demonstrated 90% reduction in phospho-S6 levels [ref]

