For patients in the cardiac and renal transplant groups, much of the risk of infection and impaired wound healing is associated with obesity, age over 40 years old, and other factors. Further, the transplant groups in which wound healing issues have been identified suffer from chronic illness and treatment with other immunosuppressive agents. To reduce the potential risk to patients with TSC in our study, we will exclude patients who are 1) obese, 2) over age 50, 3) have a history of chronic medical illness, or 4) treatment with an immunosuppressant (other than everolimus during the 7-day trial). These criteria should minimize the potential for peri-operative infection or impaired wound healing. However, we will be vigilant with the Data Safety Monitoring Plan to closely assess all patients postoperatively and record all complications, including infection and impaired wound healing. Further, we will institute a special surveillance system to monitor for these potential side effects.

The following are possible benefits that could occur through this research study:

- 1) Elimination of need for epilepsy surgery if there is a significant reduction in seizure activity;
- 2) Improvement in seizure control, as well as reduction of cognitive, behavioral, and physical injury, and sudden death risks associated with ongoing seizures;
- 3) Improvement in cognitive or behavioral function; and
- 4) Reduction in signs and symptoms of TSC (e.g., renal angiomyolipomas, lymphangiomyomatosis, facial angiofibromas).
- 5) Close medical follow-up care

CONFIDENTIAL

This document and information is the property of the NYU School of Medicine and Langone Medical Center. Do not disclose or use except as authorized in writing by the study IND sponsor

For patients with FCD, the potential benefits are likely less, but could include 1 through 3 above since increased mTOR signaling is documented in FCD and it remains uncertain if Everolimus therapy may provide clinical benefits.

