#### **4.1.1 Inclusion Criteria (Concurrent Comparison Group)**

1. Female and male patients, age 2 year to 50 years. Matched for age (+/- 7 years) and sex of subjects in the treatment group.
2. Diagnosis: treatment resistant epilepsy (> 2 failed anti-epileptic drug [AED] treatment regimens) due to TSC or FCD. Matched for diagnosis of TSC and FCD.
3. Brain surgery for seizure control in which tissue is banked for research utilizing an existing IRB-approved study.

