#### **4.4 Early Withdrawal of Subjects**

##### **4.4.1 When and How to Withdraw Subjects**

A subject may withdraw from the study due to:

- 1) Improvement in seizure activity to an extent that the patient and/or parents/legal guardians elect to forego epilepsy surgery for treatment with everolimus,
- 2) Difficult complying with protocol requirements or
- 3) A decision to withdrawal for personal reasons or adverse effects that are less severe than those that lead to mandatory discontinuation of the treatment phase.

A subject will be withdrawn from the study if any of the following are present:

- 1) The subject develops a systemic bacterial or fungal infection.
- 2) The subject develops a CTAE grade 3 or 4 (severe) event.
- 3) The patient and study will be terminated if he or she is the second case of impaired surgical wound healing or the third case of serious infection, including infection of the wound site, among the 18 everolimus-treated patients.

Given the short duration of treatment, there are no known or postulated safety concerns related to abrupt discontinuation after this duration and dosage of therapy with everolimus. Any subject who elects to withdraw from the study will be recommended to discontinue the everolimus therapy, but if they desire a tapering schedule, one will be provided with exception for those patients going forward with surgery, when everolimus will be completely discontinued prior to surgery.

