### **5.2 Treatment Regimen**

Everolimus will be self-administered (by the patient or parent at home during the 7-21 days prior to neurosurgery). The investigator will instruct the patient to take the study drug exactly as specified in the protocol.

Patients who are eligible for the active treatment group with TSC or FCD only will receive everolimus. After a minimum of three patients are treated for 7 days (Table 2), if there is no evidence of serious adverse effects or other dose-level tolerability and safety issues, we will extend the treatment duration by a maximum of one week. Again, after a minimum of three patients are treated for two weeks without evidence of serious adverse effects or other dose-level tolerability and safety issues, we will extend the treatment duration to three weeks. For patients treated longer than two weeks, an everolimus blood level will be obtained after 10-12 days and used to adjust dose to maintain a serum level of 5-10 ug/ml. to revisit escalation and numbers. If one patient at a dose duration has a serious adverse effect during a treatment cohort period (e.g., 7 days), then up to 6 patients are treated with that dose duration. If there are 2 or more serious adverse events among the 6 patients, then the duration is dropped back to the prior level. If there are no events in 3 patients or 1 event in 6 patients, then the dose duration is escalated to the next level. At the 3 week dose duration, 6 patients will be treated even if there are no events among the first 3 patients.

Table 2: Dosing Escalation for Serial Cohorts

Serial Cohort Number	Minimum # of patients if no Grade 3 or 4 adverse event or serious adverse events	Minimum # of patients if one Grade 3 or 4 adverse event or serious adverse events ^	Duration of everolimus therapy	Result of one serious adverse events including wound healing problem and serious infection	Result of two serious adverse events including wound healing problem and serious infection
1	3	9	7 days		
2	3	6	14 days	Add additional patients to Cohort 1	Return to cohort one, no potential for longer treatment duration
3	1-3	6	21 days	Add additional patients to Cohort 2	Return to cohort two, no potential for longer treatment duration

^ Adverse events as defined by CTAE v.4.0

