#### **Data Safety Monitoring Plan (DSMP)**

*Who will do the data monitoring for this study:*

- The PI, [name].
- The sub investigator, [name]
- The independent monitor, [name]

*Explain how data safety will be monitored:*

- Drug tolerability and safety will be monitored during clinical evaluations and phone visits by investigator/study team member that will seek information on adverse events by specific questioning and, as appropriate, by examination.
  - .
- [name], [name] and [name] will review all patients during the treatment period and throughout the post-treatment period. They will review all cases and if it is deemed that the serious adverse event(s) are related to study drug, the study will be terminated for that subject. If two patients among the 9 treated with everolimus develop a) impaired surgical wound healing or if three patients among the 9 develop b) serious infection, including wound site infection, study termination will occur. Any case of wound site infection complicated by a wound healing problem will NOT be considered a wound healing problem, but secondary to the infection.

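### Wound-healing and surgical-site events have no operated-patient denominator, so any dosed patient who forgoes surgery lowers the treated wound rate against controls who are all operated

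*Combined protocol and SAP*

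**What the plan says.** Section 7.3 (Subject Population(s) for Analysis) sets the safety population by dosing: "All patients who receive one or more doses of drug will be included in the analyses of safety". The next sentence defines an operated set for other purposes: "Those patients who undergo surgery will be included in the analyses of S6 phosphorylation and other measurements obtained at the time of surgery". A third sentence deals with non-completers: "Additional analyses will be conducted to compare those subjects who did not complete treatment and surgery". That comparison concerns disease and patient characteristics and does not alter the safety denominator.

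The protocol foresees treated patients without an operation. The first reason in Section 4.4.1 for which a subject may withdraw is "Improvement in seizure activity to an extent that the patient and/or parents/legal guardians elect to forego epilepsy surgery for treatment with everolimus". The first possible benefit in Section 1.5 is "Elimination of need for epilepsy surgery if there is a significant reduction in seizure activity". Neither place gives a rate. Section 4.4.2 keeps collecting safety data on patients who withdraw.

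Controls qualify through surgery. Section 4.1.1 requires "Brain surgery for seizure control in which tissue is banked for research utilizing an existing IRB-approved study", and Section 3.1 describes all 12 as undergoing routine surgery.

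Wounds are examined after the operation: at Visits 4, 5b and 6, and weekly to six weeks after surgery under Medical Monitoring (Section 6.5). The Statistical Methods text in Section 6.1 summarises safety within and across duration cohorts and sets it against the comparison group. It gives no denominator for wound events.

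**The concern.** A patient with no incision cannot have a surgical wound problem. Keeping such a patient in the denominator adds a guaranteed non-event to the treated group. The control group has no such patients, because surgery is a condition of entry. The error therefore runs one way: pre-operative everolimus looks safer for the wound than it is among those exposed to the risk.

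Section 7.3 ranks safety as the primary analysis, and Medical Monitoring singles out wound healing and wound infection as the particular worry. With nine treated patients, one patient more or less in the denominator shows in the reported rate.

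**Working it through.** **Inputs from the documents.** There are 9 treated and 12 control patients (Study Summary; Section 7.3). Section 4.4.1 still speaks of 18 treated patients; 9 is used here because the Study Summary and Section 7.3 give it. All 12 controls are operated (Sections 3.1 and 4.1.1). The plan states no wound rate by group and no rate of forgone surgery, so there is no figure of its own to reproduce.

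**Assumption.** Let m be the number of the 9 dosed patients not operated on, taken as 0, 1, 2 or 3.

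**Formulae.** With e wound events, the rate on the stated set is e/9 and the rate among patients at risk is e/(9 − m). Their ratio, (9 − m)/9, does not depend on e.

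| m | Operated | Ratio (9 − m)/9 | One event: stated set | One event: operated | Two events: stated set | Two events: operated |
|---|---|---|---|---|---|---|
| 0 | 9 | 1.00 | 1/9 = 11.1% | 1/9 = 11.1% | 2/9 = 22.2% | 2/9 = 22.2% |
| 1 | 8 | 0.89 | 11.1% | 1/8 = 12.5% | 22.2% | 2/8 = 25.0% |
| 2 | 7 | 0.78 | 11.1% | 1/7 = 14.3% | 22.2% | 2/7 = 28.6% |
| 3 | 6 | 0.67 | 11.1% | 1/6 = 16.7% | 22.2% | 2/6 = 33.3% |

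The treated rate is understated by 0%, 11%, 22% or 33% of its value. The control denominator stays at 12 throughout.

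**Zero events.** The observed rate is then 0% on either set, so only the precision differs. The plan specifies no interval. If an exact two-sided 95% interval were reported, its upper limit would be 1 − 0.025^(1/n): 33.6% for n = 9, 36.9% for n = 8 and 41.0% for n = 7. Zero events is the likeliest result at the background wound rate in Section 7.3, stated as below 2%: at 2%, 0.98^9 = 83%.

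**Effect on a test.** The plan names no test for wound events. As an illustration, take two treated events against none in 12 controls. Fisher's two-sided p is 0.171 with 9 in the denominator, 0.123 with 7 and 0.098 with 6. None crosses 0.05.

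**The case against.** The strongest reply is that the plan never says wound events will be reported as a proportion of all dosed patients. It says who enters the safety analyses, and it names no wound rate, interval or test. That is true, and the all-dosed denominator is inferred. But Section 7.3 is the only rule on who is analysed for safety, and comparing groups of 9 and 12 needs a denominator. An analyst following the text would use all dosed patients. The operated set could be stretched to cover wound outcomes only by treating findings made days to weeks later as taken at surgery.

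It is also fair to say that patients enter already scheduled for surgery and take the drug for 7 to 21 days, so few may decline. The wording in Sections 1.5 and 4.4.1 is permissive. A reader might infer that the plan expects unoperated patients; it only foresees them. Whether they would be replaced is not stated. In an open-label study of nine they would be visible in any case, and the illustrative test results do not change.

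Four stronger readings are tempting but not supported:

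- **The stopping rule is diluted.** The rule reads "If two patients among the 9 treated with everolimus develop a) impaired surgical wound healing", with three cases for serious infection. It counts cases, and an unoperated patient cannot hide one. Fewer operations mean fewer patients exposed, but a second denominator would not change that.
- **A duration cohort can be cleared on two wounds.** Section 5.2 says "If there are no events in 3 patients or 1 event in 6 patients, then the dose duration is escalated to the next level" and counts patients treated. Medical Monitoring ties safety review to patients who have completed the trial or protocol, and Section 4.4.1 treats forgoing surgery as withdrawal. The documents do not settle whether such a patient counts.
- **The rate is biased against published series.** Section 7.3 cites those rates only as the basis for its stopping thresholds and plans no comparison with them.
- **The dosed set is wrong for all safety.** General adverse events and non-surgical infections can occur before or without surgery, and for these it is the right set.

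**Conclusion.** The point holds for wound-healing problems and surgical-site infection. As written, Section 7.3 leaves patients with no incision in the treated denominator while the controls have none, so any bias lowers the treated wound rate. Its size depends wholly on how many of the nine forgo surgery, which the documents do not say. At an assumed 1, 2 or 3, the stated rate is 89%, 78% or 67% of the rate among operated patients. At none, there is no bias.

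No significance result changed in the illustration. The consequence lies in the reported wound rate and its precision, which matter in a pilot meant to describe surgical safety. The two-case and three-case stopping thresholds give no support to the point. The cohort question is a separate inconsistency between two sections, not a demonstrated error in clearance.

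**What to change.** In Section 7.3, keep all dosed patients as the set for general adverse events and non-surgical infections. Add a second safety set, patients dosed and operated on, as the denominator for wound-healing problems and surgical-site infection. State that it is compared with the operated controls, and report the number dosed but not operated beside it.

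Separately, the sponsor and the data safety monitoring committee should reconcile Section 5.2, which counts patients treated, with Medical Monitoring, which refers to patients who completed, on whether a patient without surgery counts towards a duration cohort.

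The cost is about one sentence and one extra denominator column, from data already collected. If some patients are not operated on, wound rates will look slightly less favourable and any intervals will be wider. The change is best made before outcomes are reviewed.

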#### **6.5 Stopping Rules**

A Data Safety Monitoring Program (DSMP) will be established to monitor adverse events and study safety. Prior to commencement of the study, the rate of infection and impaired wound healing associated with routine two-stage epilepsy surgeries as will be performed in this study over the past 5 years will be determined for each epilepsy surgeon ([name] and [name]). A statistician from the NYU School of Medicine Biostatistics Department will provide blinded reports to the Data Safety Monitoring Committee (DSMC). The PI, [name], [name], [name] and [name] (co-investigators) will aid in reviewing all patients during the treatment period and throughout the post-treatment monitoring period. They will review all cases and if it is deemed that the serious adverse event(s) are related to study drug, the study will be terminated for that subject. If two patients among the 9 treated with everolimus develop a) impaired surgical wound healing or if three patients among the 9 develop b) serious infection, including wound site infection. Any case of wound site infection complicated by a wound healing problem will NOT be considered a wound healing problem.

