The site of the planned surgical incision will be inspected by both of the DSMP members 5 days after initiating therapy (prior to surgery), and then at weekly intervals, beginning one week after surgery until six weeks after surgery. The neurosurgeon will document wound status with digital photography.

Blood test surveillance for possible infection will be performed at the same time intervals (7-10 days before starting everolimus, 7-21 days after starting everolimus, and 3-10 days after discharge from the hospital, and then 3 and 6 weeks after surgery if any evidence of infection is identified on examination or the post-hospital discharge blood test) consisting of a complete blood count (CBC) with differential and C-reactive protein (CRP).

Any abnormality will be documented for review by the DSMP. Since no ideal objective scoring system exists for assessing surgical site adverse events [39,40], any wound breakdown, dehiscence or infection will be considered a serious adverse event, and will be reported to the participating site IRB and to the NINDS, and the decision will be made as to whether the study should be terminated.

Individual subject participation in the study will be terminated if the DSMC finds any of the following unexpected new findings in a subject:

- 1) Documented wound infection requiring surgery
- 2) Documented wound dehiscence requiring surgery
- 3) Persistent fever above 101 degrees F and abnormally elevated serum wbc count and ESR and CRP in the absence of a known cause
- 4) Documented bacterial meningitis

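### The attribution of healing problems in infected wounds ignores order of onset and is worded differently across sections, so failed wounds that later become infected can miss both automatic termination counts

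*Combined protocol and SAP*

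**What the plan says.** The sample size text under section 7.3 states that "For this preliminary study, safety analyses are primary". The study is to terminate if "among the 9 treated subjects, there are two cases of wound healing problems or three cases of serious infection, including wound site infection". The same text adds that, when the wound site is infected, "any problems with wound healing will be considered secondary to the infection and NOT as a primary wound healing problem". The Study Summary (Statistical Methodology) repeats this. Neither place refers to which event came first.

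Section 6.5 (Stopping Rules) words the exclusion differently: "Any case of wound site infection complicated by a wound healing problem will NOT be considered a wound healing problem". The Data Safety Monitoring Plan in section 7.1 says that such a case "will NOT be considered a wound healing problem, but secondary to the infection". Both describe an infection that is then complicated, which may mean infection first, but neither defines the order.

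Section 4.4.1 ends the study at the second case of impaired surgical wound healing or the third serious infection, wound infection included. It has no exclusion for infected wounds and counts among 18 treated patients.

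Under Medical Monitoring, "any wound breakdown, dehiscence or infection will be considered a serious adverse event", and each such event leads to a decision on whether to terminate. No numerical limit is attached to that decision.

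**The concern.** The exclusion seems meant to avoid charging everolimus with a healing failure when infection caused the breakdown. The sample size wording goes further and also covers a wound that opened first and was infected afterwards. That sequence is foreseeable here: section 1.5 names wound healing and infection as the potential risks of treatment, and section 5.3.1.5 describes the drug as immunosuppressive.

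Healing has the lower limit, so each reclassified case moves to a count that takes one more event to reach. The sections also allow different classifications of the same patient. Whoever applies the rule would have to choose a section after seeing the case. At stake is whether the automatic counts respond to the harm they were set up to detect.

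**Working it through.** **1. Three records under the sample size wording (days are illustrative)**

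- Infection on day 5, dehiscence on day 8: infection only. This fits the apparent intent.
- Dehiscence on day 5, never infected: healing problem. This also fits.
- Dehiscence on day 5, infected on day 9: infection only. The section 6.5 wording, read as infection first, would leave it a healing problem. Section 4.4.1 would count it as impaired healing, because it has no exclusion.

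**2. Counting, with no assumed rates**

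Two patients who dehisce and are then infected score 0 healing problems (limit 2) and 2 infections (limit 3). Adding one uninfected failure gives 1 and 2. So 3 of 9 treated patients (33%) have failed wounds and neither limit is reached. Three is the maximum: a second uninfected failure reaches the healing limit, and a third infected one reaches the infection limit.

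**3. Inputs for the size**

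- From the plan: n = 9; limits 2 and 3; background healing problems below 2%; mean infection rate 5.3% (range 1.6–8.6%).
- Assumed: true healing-failure rate p of 2%, 10% or 20%; fraction f of failures later infected of 25%, 50% or 75%. The documents give neither quantity.

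The plan states no probability of reaching its limits, so there is no figure to reproduce. At its background rates the binomial gives P(at least 2 of 9 at 2%) = 1.3% and P(at least 3 of 9 at 5.3%) = 1.0%.

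**4. Model**

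Each patient falls into one of four classes:

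- X, healing failure, uninfected: p(1 − f)
- Y, healing failure, then infected: p·f
- W, infection without a prior healing failure: (1 − p) × 0.053
- neither: the remainder

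The as-written rule is reached if X ≥ 2 or Y + W ≥ 3. For comparison, healing-first cases are kept in the healing count: X + Y ≥ 2 or W ≥ 3. Both are exact multinomial sums over 9 patients.

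**5. Healing count alone, p = 20%, f = 50%**

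- As written (rate 0.20 × 0.50 = 0.10): 1 − 0.9⁹ − 9 × 0.1 × 0.9⁸ = 22.5%
- Kept in the healing count (rate 0.20): 1 − 0.8⁹ − 9 × 0.2 × 0.8⁸ = 56.4%

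**6. Either count reached**

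| p | As written, f = 25% | f = 50% | f = 75% | Healing-first kept in healing count |
|---|---|---|---|---|
| 2% | 1.9% | 1.9% | 1.9% | 2.2% |
| 10% | 16% | 12% | 11% | 23% |
| 20% | 43% | 33% | 30% | 57% |

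With f = 0 the two rules agree. Applying 5.3% to all patients, and counting healing-first cases toward both limits, gives 35.2% as written against 58.2% at p = 20%, f = 50%. The conclusion is the same.

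**The case against.** The strongest reply is that nothing disappears. A reader might infer that the rule erases the dehiscence, and the documents do not support that. The case counts toward the infection limit. It is a serious adverse event with its own termination decision. It goes to the DSMB if possibly related to the study, and safety data go there after every three patients in any case. Table 2 in section 5.2 pools healing problems and serious infections for duration escalation, so two such cases reverse escalation under either label. All of this stands. What can be missed is the automatic count, and the case-by-case decision has no threshold to replace it.

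A reader might also infer that the reported healing rate will be biased down and then judged against the 2% background. The plan does not say so. The attribution sentence qualifies the termination counts, and nothing extends it to the safety tables. Section 6.1 plans a descriptive safety summary compared with the comparison group, and no test against 2% is planned. It is fair to say only that the plan does not state how a case with both events will appear in that summary.

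The larger losses also depend on failure rates at least five to ten times the background figure and on an unsourced fraction later infected. That is correct, and the 2% row shows almost no loss.

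Finally, placing each case in a single class, by whichever event was documented earlier, has a gap of its own. One dehisced-then-infected case plus two other infections makes three infections as written and reaches the limit. Under single-class counting it scores 1 and 2 and does not. Order of onset is not proof of cause either, and Medical Monitoring concedes that no ideal objective scoring system exists.

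**Conclusion.** The point holds in a limited form. The sample size text and the Study Summary ignore order of onset. Section 6.5 and the Data Safety Monitoring Plan can be read more narrowly, though their wording may only restate the same rule. Section 4.4.1 is the clearest conflict, with no exclusion and a different denominator.

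The result that 3 of 9 failed wounds can reach neither limit follows from the literal text and needs no assumed rate. The probabilities rest on assumed p and f, on independent patients, and on all 9 treated patients having surgery. On those terms the loss is about 0.3 percentage points at 2% (2.2 − 1.9), 7 to 12 points at 10% (23 − 16 to 23 − 11) and 14 to 27 points at 20% (57 − 43 to 57 − 30). The weakness therefore matters only if everolimus impairs healing, which is the situation the healing limit is there to detect. The other safeguards reduce the consequence, so this should be corrected but does not undermine the trial.

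**What to change.** In the safety analysis, tabulate for both groups every wound-healing problem whether or not the wound was infected, and every wound infection. Cross-classify the cases by which was documented first, with a category for simultaneous or unknown order. A case with both events then appears in both rows, and no attribution of cause is needed.

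Separately, the sponsor and the DSMC must reconcile the Study Summary, section 4.4.1, the sample size text under section 7.3, section 6.5 and the Data Safety Monitoring Plan. They need one statement of how a case with both events counts toward termination, and one denominator (9 or 18). No particular termination rule is proposed here.

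The cost is one or two table rows and consistent wording in five places. Adverse event start dates are already collected (section 6.2.1), and wounds are already assessed in both groups in hospital and 3 to 10 days after discharge (Visits 4, 5b and 6). Order will stay uncertain in some cases, partly because the photographs at those visits are of the surgical site dressing. The extra category is there for those cases.
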